# 6.10.1.5. European Quality of Life Five-Dimension Five-Level Scale

The EQ-5D-5L is a standardized instrument for use as a measure of health outcomes (see Appendix 6). Mobility, self-care, usual activities, pain/discomfort, and anxiety/depression are each assessed on a 5-level categorical scale.

Patients will complete the EQ-5D-5L questionnaire at the site at the Baseline Day 1 visit and the Week 24 visit before other types of study procedures, such as blood draws and physical examinations, are performed. The EQ-5D-5L will be completed on a tablet device at the study site.

# 6.10.1.6. Patient Global Assessment and Patient Global Impression of Change

These simple questions are used by the patient to qualitatively describe severity of pain or effects on function (PGA) or impression of change in pain severity (PGIC) (see Appendix 3) on a schedule described in the Schedule of Activities (Section 1.1). Patients should answer these questions before other types of study procedures, such as blood draws and physical examinations, are performed. At the Screening visit, the Endometriosis-Associated Pain Severity (see boxed item in Section 6.2) will be completed prior to the PGA. The PGA for pain severity and the PGIC will be completed on a tablet device at the study site. The PGAs for dysmenorrhea, NMPP, and function will be completed on a paper questionnaire at the study site.

### 6.10.1.7. Endometriosis Health Profile Work Domain

This 5-question paper questionnaire will be completed by the patient to describe the effects of endometriosis on their work (Appendix 5). Patients will complete the EHP Work Domain questionnaire at the site at the Baseline Day 1 visit and Week 24 visits before other types of study procedures, such as blood draws and physical examinations, are performed.

# **6.10.1.8.** Status of Menstruation Recovery

If the patient does not continue into the extension study (MVT-601-3103), and the first menstruation after the end of study treatment administration is observed before the Follow-Up visit, the date of onset of the first menstruation is recorded in the electronic case report form

(eCRF). Patients whose menses has not resumed as of the Follow-Up visit for whom there is no explanation for the lack of resumption (eg, medical procedure or medications) will be contacted again by telephone (see Section 6.8).

#### 6.10.1.9. **Pharmacogenomics Sample Collection**

For possible exploratory investigation of markers enabling the prediction of drug response, a sample of blood will be collected and stored for future pharmacogenomics analyses, unless precluded by local law or regulations. All patients will be eligible for collection of the pharmacogenomics sample, however, the sample may only be obtained and stored from patients who provide a separate informed consent form for pharmacogenomics sample collection. Patient participation in the pharmacogenomics research is voluntary and refusal to participate will not preclude entry into the study or indicate withdrawal from the study.

If possible, the pharmacogenomics sample should be drawn from consented patients at the Baseline Day 1 visit, but it may be drawn at any time during the study through Week 24/Early Termination (inclusive). Patients can request their sample to be destroyed at any time. A pharmacogenomics sample should not be collected from any patient who has received comparable bone marrow transplant or whole blood transfusion within 6 months before sample collection. Refer to the Study Reference Manual for directions on collecting, handling, and storage of pharmacogenomics samples.

#### 6.10.1.10. Genomics Sample Collection

For investigating endometriosis disease markers, samples of blood will be collected for DNA and micro-ribonucleic acid (miRNA) analyses, unless precluded by local law or regulations. All patients will be eligible for collection of the genomics samples, however, the samples may only be obtained and stored from patients who provide a separate informed consent form for genomics sample collection. Patient participation in the genomics research is voluntary and refusal to participate will not preclude entry into the study or indicate withdrawal from the study.

Patients can request their samples to be destroyed at any time. Genomics samples should not be collected from any patient who has received a bone marrow transplant or whole blood transfusion within 6 months before sample collection. Refer to the Study Reference Manual for directions on collecting, handling, and storage of genomics samples.

#### 6.10.2. **Safety-Related Procedures**

#### 6.10.2.1. **Vital Signs**

Vital signs, including blood pressure, respiratory rate, heart rate, and temperature, should be measured in the seated position after 5 minutes of rest.

#### Weight and Height 6.10.2.2.

Patients should have weight and height measured while wearing indoor clothing and with shoes removed.

#### 6.10.2.3. Physical and Gynecologic Exams and Papanicolaou Test

A complete physical examination will include head, ears, eyes, nose, mouth, thyroid, skin, heart and lung examinations, lymph nodes, gastrointestinal, skeletal, and neurological systems. All subsequent (ie, post-randomization) physical examinations should focus on signs and symptoms reported by the patient to assess for clinically significant changes from the Baseline assessment. The gynecologic examinations will include breast and pelvic exams. A Papanicolaou test must be conducted for women without an available test result from within 2 years prior to the Screening visit. Re-measurement should be performed for inadequate samples or potential false-positive results.

#### 6.10.2.4. Endometrial Biopsy

An endometrial biopsy will be performed using an endometrial suction curette (eg, Pipelle®) and submitted to the central laboratory for reading. Local anesthetics may be given for endometrial biopsies according to the investigator's discretion. If the biopsy is inadequate for diagnosis, it should be repeated and sample submitted to the central laboratory. If the second specimen is also inadequate, the patient is not eligible for the study.

#### **6.10.2.5.** Visual Acuity

Presenting visual acuity must be assessed with the supplied study eye chart. If the patient uses corrective lenses, she should wear her usual prescription glasses or contact lenses during the assessment, and the same prescription lenses should be worn during the assessment, and subsequent visual testing. Perform the visual acuity testing using the entire eye chart. Do not stop at a visual acuity of 100 – continue as far as the patient can go per the testing instructions (see Study Reference Manual for additional details).

Patients whose presenting visual acuity score is 90 or lower at the Screening visit should be encouraged to obtain a diagnostic evaluation from an eye care provider, ie, an ophthalmologist or an optometrist. Any findings (ie, diagnoses) from the eye examination should be recorded as medical history.

If a treatment or correction was made to treat visual acuity (eg, stronger eyeglasses) prior to the first dose of study drug, repeat the presenting visual acuity testing with the new correction (eg, with the new corrective lenses). For patients whose presenting visual acuity score has declined at the Week 24/Early Termination visit, please see Section 6.8 for follow-up requirements.

#### 6.10.2.6. Electrocardiograms

ECGs (12-lead) will be obtained at the time points described in the Schedule of Activities (Section 1.1). ECGs will be measured using standardized equipment provided by central core laboratory with the patient in a semi-supine or supine position after 5 minutes of rest. The ECGs will be assessed by central review and a report provided to the site. The investigator or sub-investigator (or a qualified individual at the investigational site) will interpret the ECG report provided by the central reviewer using one of the following categories: normal or abnormal.

The investigator or sub-investigator will judge if any of the findings are clinically significant.

The Baseline Day 1 QTcF may be assessed locally for purposes of eligibility determination.

#### 6.10.2.7. Clinical Laboratory Samples

All protocol-required laboratory assessments must be conducted in accordance with the Study Laboratory Manual and the protocol Schedule of Activities (see Section 1.1). Laboratory requisition forms must be completed and samples must be clearly labelled with the Patient ID number, protocol number, site/center number, and visit date. Details for the preparation and shipment of samples will be provided. Reference ranges for all safety parameters will be provided to the site by the central laboratory.

The samples collected for clinical laboratory tests are listed in Table 6-1.

**Table 6-1** Clinical Laboratory Tests

Chemistry	Hematology	Urinalysis
Potassium	White blood cell count	Protein
Chloride	White blood cell differential	Glucose
Bicarbonate	Red blood cell count	Blood
Blood urea nitrogen	Hemoglobin	Urobilinogen
Creatinine	Hematocrit	Bilirubin
Glucose	Mean corpuscular volume	Color and clarity
Calcium	Platelet count	рН
Phosphate	Red blood cell morphology	Leucocyte esterase
Magnesium		Ketones
Sodium		Nitrite
Albumin		Specific gravity
Creatinine kinase		Urine Microscopy
Hemoglobin A1c		
Bilirubin total		
Alanine aminotransferase		
Aspartate aminotransferase		
Gamma-glutamyl transferase		
Alkaline phosphatase		
Lipids	Serology	Pregnancy
Total cholesterol	Hepatitis A antibody	Pregnancy test (human
Low density lipoprotein	Hepatitis B surface antigen	chorionic gonadotropin)
High density lipoprotein	Hepatitis B core antibody	
Triglycerides	Hepatitis C antibody	

Hormones	
Thyroid-stimulating hormone	
Prolactin	
Luteinizing hormone	
Follicle-stimulating hormone	
Estradiol	
Progesterone	
25 (OH) vitamin D	

A separate sample will be collected at the Baseline Day 1 visit in all patients and will be banked and tested for presence of hepatitis A, B, and C (hepatitis A antibody, IgM, hepatitis B core antibody, IgM, hepatitis B surface antigen, hepatitis C antibody, and hepatitis C RNA) for evaluation of abnormal liver tests in the future, if requested by the medical monitor.

The central laboratory will perform laboratory tests for chemistry, hematology, urinalysis, serology, and serum hormone levels. Each study site will conduct urine pregnancy tests locally.

All laboratory tests with values that are considered abnormal and clinically significant during participation in the study or within 30 days after the last dose of study drug should be repeated until the values return to normal, baseline, or have stabilized. Abnormal values, determined to be clinically significant, should be reported as adverse events.

The investigator will maintain a copy of the reference ranges (with the record of the reference ranges) for the laboratory or laboratories used.

#### **6.10.2.8.** Bone Mineral Density

Bone mineral density is determined using DXA scanning and will be assessed at the lumbar spine (L1, L2, L3 and L4), total hip, and femoral neck (same leg within each patient) at the time points described in the Schedule of Activities (Section 1.1). The scans will be read by the central radiology laboratory in accordance with the imaging charter. Training, quality review, and readings will be done by a central radiology laboratory as described in the central radiology charter for bone mineral density.

Throughout the study, the same DXA apparatus will used at each site and operated in the same scan mode for all scans for an individual patient. The central radiology laboratory will collect and evaluate all DXA scans for acceptability. Bone mineral density changes for individual patients will be monitored by the central radiology laboratory over the course of the study. Investigators will be notified if a patient experiences a bone mineral density loss from baseline of 7% or more at any of the anatomical sites assessed during the study. In this case, it is at the investigator's discretion to consider the patient's status and determine future management. Detailed instructions for DXA scanning are provided in the Study Reference Manual.

Please see Section 6.8 for follow-up of patients whose bone mineral density has decreased by > 2% at the lumbar spine (L1-L4) or total hip at the Week 24/Early Termination visit or most recent study scan relative to Baseline (Run-In Period).

#### 6.11. Biological Sample Retention and Destruction

Biological samples present at the conclusion of this study may be retained in storage by the sponsor for a period up to 10 years for purposes of this study. Samples collected for pharmacogenomics and genomics testing (see Sections 6.10.1.9 and 6.10.1.10) will be stored frozen at an appropriate vendor facility identified by the sponsor.

The need to conduct pharmacogenomics analyses or additional genomics analyses for endometriosis markers may be identified after this study (or additional studies) has been completed. For this reason, the collected samples will be retained for up to 10 years after the last patient completes the study. A patient may request the destruction of her samples at any time. The sponsor may destroy the samples sooner than 10 years after the study completes.

#### 7. SAFETY CONSIDERATIONS

Study assessments of safety include adverse events, physical examinations, vital signs (and weight), ECGs, bone mineral density assessments, and clinical laboratory tests.

#### 7.1. Adverse Event Definitions

#### 7.1.1. Adverse Event

Adverse event: An adverse event is any unfavorable and unintended sign (including an abnormal laboratory finding), symptom, or disease (new or exacerbated) temporally associated with the use of a medicinal product, whether or not related to the medicinal product.

Events meeting the definition of an adverse event **include**:

- A worsening, excluding minor fluctuations, in the nature, severity, frequency, or duration of a pre-existing condition;
- Development of an intercurrent illness during the study;
- Development of symptoms that may or may not be related to the use of a concomitant medication or investigational product;
- Injury or accidents: If a medical condition is known to have caused the injury or accident, the medical condition and the accident should be reported as 2 separate medical events (eg, for a fall secondary to dizziness, both "dizziness" and "fall" should be recorded separately); and
- An investigational abnormality (eg, laboratory parameter, vital sign, ECG) only if the abnormality is considered clinically significant by the investigator based on at least one of the following criteria:
  - o Induces clinical signs or symptoms;
  - o Requires active intervention;
  - o Requires interruption or discontinuation of study drug.

Events that **do not** meet the definition of an adverse event include:

• Medical or surgical procedures (eg, surgery, endoscopy, tooth extraction, transfusion); the condition that leads to the procedure is an adverse event;

- Pre-existing diseases or conditions present or detected before the start of study drug administration that do not worsen:
- Situations where an untoward medical event has not occurred (eg, planned hospitalization for an elective procedure, with elective defined as known or planned at the time of signing of the informed consent);
- Endometriosis-associated pain is not considered an adverse event in this study because it is being quantitatively measured as the primary efficacy endpoint.

Adverse events that occur during the study should be evaluated by the investigator and graded according to the National Cancer Institute Common Terminology Criteria for Adverse Events (CTCAE). Episodic adverse events, such as vomiting, or those that occur repeatedly over a period of consecutive days are "intermittent". All other events are "continuous". Additional information on detecting, documenting, and reporting adverse events and serious adverse events are provided below.

#### 7.1.2. Serious Adverse Event

A serious adverse event is any untoward medical occurrence that, at any dose:

- a. Results in death;
- b. Is life-threatening;

NOTE: The term "life-threatening" in the definition of "serious" refers to an event in which the study participant was at risk of death at the time of the event. It does not refer to an event, which hypothetically might have caused death, if it were more severe. For example, drug-induced hepatitis that resolved without evidence of hepatic failure would not be considered life-threatening even though drug-induced hepatitis can be fatal.

c. Requires hospitalization or prolongation of existing hospitalization;

NOTE: In general, hospitalization signifies that the patient has been detained at the hospital or emergency ward for observation and/or treatment that would not have been appropriate in the physician's office or out-patient setting. Complications that occur during hospitalization are adverse events. If a complication prolongs hospitalization or fulfills any other serious criteria, the event is serious. When in doubt as to whether "hospitalization" occurred or was necessary, the adverse event should be considered serious. Hospitalization for elective treatment of a pre-existing condition that did not worsen from baseline is not considered an adverse event.

d. Results in persistent or significant disability/incapacity;

NOTE: The term disability means a substantial disruption of a person's ability to conduct normal life functions. This definition is not intended to include experiences of relatively minor medical significance such as uncomplicated headache, nausea, vomiting, diarrhea,

Effective: 12-MAR-2018

influenza, and accidental trauma (eg, sprained ankle) which may interfere or prevent everyday life functions but do not constitute a substantial disruption.

- e. Is a congenital anomaly/birth defect;
- f. Important medical events which jeopardize the patient and may require medical or surgical intervention to prevent one of the outcomes listed above. Examples of such events are invasive or malignant cancers, intensive treatment in an emergency room or at home for allergic bronchospasm, blood dyscrasias or convulsions that do not result in hospitalization, or development of drug dependency or drug abuse.

### 7.2. Adverse Event Reporting

The reporting of serious adverse events by the sponsor (Myovant Sciences GmbH) to regulatory authorities is a requirement and each authority has a timetable for reporting these events based upon established criteria. Likewise, it is the responsibility of the investigator to report serious adverse events to their local Institutional Review Board (IRB) or Independent Ethics Committee (IEC).

Care will be taken not to introduce bias when detecting adverse events and/or serious adverse events. Open-ended and non-leading verbal questioning of the patient is the preferred method to inquire about adverse event occurrence. Appropriate questions include:

- "How are you feeling?"
- "Have you had any (other) medical problems since your last visit/contact?"
- "Have you taken any new medicines, other than those provided in this study, since your last visit/contact?

The patient's eDiary entries, including bleeding and answers to the other patient-reported outcome measures, will not be used as a primary means to collect adverse events, however they should be reviewed by the study site personnel and the study monitors. Should the investigator or site staff become aware of a potential adverse event through the information collected with these instruments, proper follow-up with the patient for medical evaluation should be undertaken. Through this follow-up, if it is determined that an adverse event not previously reported has been identified, normal reporting requirements should be applied.

All patients who experience an adverse event will be evaluated at appropriate time intervals until the event resolves or has stabilized or become chronic. At the conclusion of the study, the investigator and medical monitor will assess unresolved adverse events and determine if additional follow-up is warranted.

All adverse events, whether or not related to the study drug treatment, must be fully and completely documented on the adverse event case report form and in the patient's source documents. In addition, any adverse event resulting in permanent treatment discontinuation must be recorded on the appropriate case report form as well as documented in the patient's source documents. Adverse event terms should include a diagnosis, as available, in preference to listing the individual signs and symptoms. If the diagnosis is not known, the investigator should record each sign and symptom as an individual adverse event.

Overdose and pregnancy in the patient will be reported as described in Section 7.7 and Section 7.8, respectively.

#### 7.2.1. Adverse Event Reporting Period

Adverse events will be collected from the time the first dose of single-blind study drug is administered in the Run-In Period through the double-blind Randomization Treatment Period and until the Follow-Up visit (approximately 30 days after the last dose of study drug) or the date of initiation of another investigational agent or hormonal therapy affecting the hypothalamic-pituitary-gonadal axis or surgical intervention for endometriosis, whichever occurs first, as also specified in the study Schedule of Activities (Section 1.1). For patients entering the extension study, adverse event collection for this study will end at the Week 24 visit. Study procedure-related adverse events will be collected from the signing of the informed consent form.

Serious adverse events will be collected from the signing of the informed consent form until the safety follow-up visit (approximately 30 days after the last dose of study drug). For patients entering the extension study, serious adverse event collection for this study will end at the Week 24 visit. Serious adverse events reported to the investigator after the safety reporting period should be reported to the sponsor if the investigator assesses the event as related to the study drug treatment.

With the exception of events that are considered related to study screening procedures, (which are to be recorded as adverse events), events occurring between signing of the informed consent form and the first dose of study drug will be recorded as medical history and in the patient's clinical record for any patient who continues to meet eligibility criteria and proceeds to dosing with study drug.

Reporting instructions for serious adverse events are provided in Section 7.6.

#### 7.3. Assigning Causal Relationship to Study Drug

The reasonable possibility of the relationship of an adverse event to study drug(s) is to be assessed with careful medical consideration at the time of evaluation of an adverse event. The following definitions are to be used for the relationship of the adverse event to study drug:

- **Probably related**: A clinical event, including laboratory test abnormality, with a reasonable time sequence to administration of the drug, unlikely attributed to concurrent disease or other drugs or chemicals, and that follows a clinically reasonable response on readministration (rechallenge) or withdrawal (dechallenge).
- **Possibly related**: A clinical event, including laboratory test abnormality, with a reasonable time sequence to administration of the drug but that could also be explained by concurrent disease or other drugs or chemicals. Information on drug withdrawal may be lacking or unclear.
- **Not related**: A clinical event, including laboratory test abnormality, with a temporal relationship to drug administration that makes a causal relationship improbable and/or in which other drugs, chemicals, or underlying disease provide a plausible explanation.

All adverse events, whether or not related to study drug, must be fully and completely documented on the adverse event page of the eCRF and in the patient's clinical record. In the event a patient is withdrawn from the study because of an adverse event, it must be recorded on the eCRF as such.

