#### 9.5. Safety Analyses

Safety analyses will be conducted using the Safety Population and summarized by treatment group as treated. The treatment-emergent period will be defined as the period of time from the first dose date and time of the randomized study drug treatment through 30 days after the last dose of study drug, or the date of initiation of another investigational agent or hormonal therapy affecting the hypothalamic-pituitary-gonadal axis or surgical intervention for endometriosis, or the date and time of the first dose of open-label extension (MVT-601-3103) study drug, whichever occurs first. Safety will be assessed through summaries of adverse events, the frequency of treatment discontinuations due to adverse events, laboratory evaluations, and bone densitometry results.

The severity of all adverse events is to be evaluated by the investigator based on the National Cancer Institute CTCAE. All adverse events will be coded to preferred term and system organ class using MedDRA 20.0 or higher. The incidence of adverse events will be presented by MedDRA system organ class and preferred term, relationship to study drug treatment, and severity. A patient reporting the same adverse event more than once is counted once, and at the maximum severity or strongest relationship to study drug treatment when calculating incidence.

Laboratory data consist of chemistry, hematology, and hormonal tests. Only data collected by the central laboratory will be used to do the analyses. The National Cancer Institute CTCAE, will be used to categorize toxicity grade for the laboratory parameters. Shift tables will be provided for each gradable parameter to summarize baseline toxicity grade versus post-baseline toxicity grade. For laboratory parameters that are not gradable by the CTCAE, a shift table based upon the normal range (low, normal, and high) will be provided for each parameter to summarize the Baseline versus post-baseline results. All data will be listed and summarized by visit. The change from Baseline to each post-baseline study visit will be presented by treatment group for each laboratory test.

For vital signs parameters, including temperature, all data will be listed and summarized by visit. The change from Baseline to each post-baseline study visit will be presented by treatment group for each parameter.

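### Section 7.3: an event with reasonable timing and another possible cause meets both *Possibly related* and *Not related*, so the counts of adverse events by relationship are not well defined

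*Protocol*

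**What the plan says.** Section 7.3 asks the investigator to place each adverse event in one of three categories.

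- *Probably related* needs reasonable timing, an alternative cause being unlikely, and a supportive response when the drug is stopped or given again.
- *Possibly related* is an event "with a reasonable time sequence to administration of the drug but that could also be explained by concurrent disease or other drugs or chemicals". The definition adds that withdrawal information may be missing or unclear.
- *Not related* has two limbs. The first is an event "with a temporal relationship to drug administration that makes a causal relationship improbable". The second limb, which follows directly, reads: "and/or in which other drugs, chemicals, or underlying disease provide a plausible explanation".

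The only general guidance is the opening sentence: "The reasonable possibility of the relationship of an adverse event to study drug(s) is to be assessed with careful medical consideration". The section gives no order of precedence.

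The assigned category is used in three places.

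- Section 9.5, and in similar terms the synopsis under Safety: "The incidence of adverse events will be presented by MedDRA system organ class and preferred term, relationship to study drug treatment, and severity".
- Section 9.5, for a patient who reports the same event more than once: the event is counted once, "at the maximum severity or strongest relationship to study drug treatment when calculating incidence".
- Section 7.2.1, for serious events that come to light after the safety reporting period: they "should be reported to the sponsor if the investigator assesses the event as related to the study drug treatment".

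**The concern.** Reasonable timing together with another possible explanation is an ordinary combination in this trial. Headache is listed as an identified adverse reaction (Sections 2.2.4.2 and 7.10) and often has other explanations. If such an event satisfies two definitions, two investigators can code the same facts differently and both comply with the protocol. The synopsis plans about 160 sites, so uniform practice cannot be assumed.

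The investigator assigns the category at the site. A statistical analysis plan can say how to tabulate what was coded, but it cannot recover which definition the investigator applied. The table of events by relationship would then partly reflect coding habit. For a late serious event, the choice of definition could decide whether a report is made at all.

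**Working it through.** No figure in the protocol is at issue, so the check is logical. Let T be a reasonable time sequence and A a plausible alternative cause. From Section 7.3:

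- *Possibly related* = T and A.
- *Not related* = (timing makes causality improbable) and/or A. Under the 'or', A alone is sufficient.

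Each combination can then be placed:

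| Timing | Alternative cause | Category met |
|---|---|---|
| Reasonable | Yes | *Possibly related* and *Not related* |
| Improbable | Yes | *Not related* only |
| Improbable | No | *Not related* only |
| Reasonable | No, with supportive response to withdrawal or re-administration | *Probably related* only |
| Reasonable | No, with no such information | None, read strictly |

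**First row.** If the alternative-cause wording in the two definitions means the same thing, every event that meets *Possibly related* also meets *Not related*. The overlap is then the whole middle category, not an edge case.

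**Last row.** This is a small gap next to the overlap. The remark on missing withdrawal information suggests that *Possibly related* is the intended home, but its defining clause asks for another explanation.

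**Effect on the counts.** For a given event term, let p be the number of patients who are unambiguously *Probably related*, and m the number whose strongest rating falls in the first row. If every investigator reads *Possibly related* first, p + m patients appear with some drug relationship. If every investigator reads *Not related* first, only p do. The count can lie anywhere from p to p + m. The protocol gives neither p nor m, so the width cannot be stated.

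**The one-word remedy.** Replace 'and/or' by 'and', so that *Not related* = (timing improbable) and A. The first row becomes *Possibly related* only, as wanted. The third row, improbable timing with no alternative, then falls in no category, because both other definitions require reasonable timing. An overlap is exchanged for a gap.

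**Where the category does not matter.**

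- Section 7.6: serious events are reported within 24 hours whatever the investigator's view of causality.
- Section 7.5: an ALT or AST rise of at least 3 x ULN in the Randomized Treatment Period or at the Follow-Up visit goes to the sponsor within 24 hours, with no causality condition.
- Sections 7.2 and 7.3: every adverse event is documented, related or not.
- Section 9.3: no efficacy analysis uses the category.

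**The case against.** **The two definitions can be told apart by judgement.** In *Possibly related* the event might *also* have another cause, so the drug is still a candidate. In *Not related* the other cause supplies the explanation. The opening sentence makes reasonable possibility the test. This is a fair reading, probably the intended one, and it narrows the ambiguity. It does not remove it: the *Not related* definition asks only for a plausible explanation, not one that displaces the drug, and no sentence ranks the categories.

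**The consequences are small.** Much of this stands. Safety analysis is descriptive (synopsis, Safety), and incidence is also given by system organ class and preferred term. Investigators are blinded during randomized treatment (Section 5.8), so the same loose wording applies to all arms; inconsistent or understated counts are the concern, not an expected bias between arms. The strongest-relationship rule matters only when a patient repeats an event.

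The late serious-event condition starts about 30 days after the last dose. With the relugolix half-life of 37 to 42 hours (Section 2.2.4.1), 30 x 24 = 720 hours is 720/42 = 17.1 to 720/37 = 19.5 half-lives, so timing alone will settle many of these events. Delayed effects remain possible. For patients entering the extension, collection for this study ends at the Week 24 visit, so the 30-day argument does not cover them.

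**Stronger readings.** A reader might infer that the overlap reaches the liver rechallenge rule, because Section 7.5.1 speaks of abnormalities possibly caused by the drug. The text does not support that: the section sets its own conditions, requires investigator and sponsor to agree, and does not refer to the Section 7.3 categories. A reader might also infer that serious or liver events could go unreported during the study. Sections 7.5 and 7.6 rule that out.

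**Conclusion.** The definitions are wrong as written. Through 'and/or', a plausible alternative cause alone satisfies *Not related*, so an event with reasonable timing and another possible cause belongs to two categories at once. The overlap covers all of *Possibly related* if the two alternative-cause phrases are taken as equivalent, and part of it if investigators distinguish them by judgement.

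The main effect is a descriptive incidence by relationship that may be inconsistent and understated. A minor effect is uncertainty over which late serious events are reported. Neither can be sized from the protocol. The severity is low: the point is worth correcting, but the trial's conclusions on efficacy do not depend on it.

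**What to change.** Reword Section 7.3 so that each event fits exactly one category.

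- *Not related*: the timing makes a causal relationship improbable, or another cause explains the event so that no reasonable possibility of a drug cause remains.
- *Possibly related*: the timing is reasonable and the drug remains a candidate, but the conditions for *Probably related* are not met. This keeps the overlapping events in one place and also takes in those with reasonable timing, no other explanation and no withdrawal information.
- Do not simply change 'and/or' to 'and'.

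In Section 7.2.1, state whether 'related' includes *Possibly related*.

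The cost is a short wording amendment and matching eCRF guidance to sites. Related-event counts may rise slightly.
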